10.3 Method of Assigning Subjects to Treatment Groups

This is an open-label study. Randomization is not required because all subjects will be treated identically in the Treatment Cohort.

Subjects in the Observational Cohort will not receive study drug.

10.4 Dose Modification for Use With Concomitant CYP3A Inhibitors (Treatment Cohort)

The dosage of VX-661/ivacaftor can be altered only when co-administered with moderate or strong inhibitors of CYP3A.

Table 10-2 Dosing Recommendations for Subjects Taking Concomitant CYP3A Inhibitors

Type of Inhibitor	Example of Inhibitor	VX-661 100 mg/Ivacaftor 150 mg	Ivacaftor 150 mg
Strong CYP3A inhibitor	ketoconazole, itraconazole, posaconazole, voriconazole, telithromycin, and clarithromycin ^a	One tablet twice a week in the morning (3 to 4 days between doses)	No evening dose
Moderate CYP3A inhibitor	fluconazole, erythromycin	One tablet of VX-661 100 mg/ivacaftor 150 mg or one ivacaftor 150 mg in the morning, taken on alternate days. No evening dose.	

^a A more detailed but nonexhaustive list of study prohibitions and cautions for food and medication will be provided in the Study Reference Manual.

The dosage of VX-661/ivacaftor cannot be otherwise altered, but the investigator can interrupt or stop treatment ([Sections 10.5](#) and [10.6](#)).

10.5 Study Drug Interruption (Treatment Cohort)

If study drug dosing must be interrupted for more than 72 hours, the medical monitor must be notified. In these instances, study drug dosing may only resume after approval by the medical monitor. Specific instructions for interruption for elevated LFT levels and increased QTc intervals are provided in [Section 11.8.6](#) and [Section 11.8.4](#), respectively.

Missed Doses

If a subject misses a dose and recalls the missed dose within 6 hours, the subject should take his/her dose with food. If more than 6 hours have elapsed after his/her usual dosing time, the subject should skip that dose and resume his/her normal schedule for the following dose. For example,

- if the morning dose of study drug should have been taken at approximately 08:00, and the subject remembers at 12:00 that he/she forgot to take his/her dose, he/she should take the dose with food as soon as possible.
- if the morning dose of study drug should have been taken at approximately 08:00, and more than 6 hours have elapsed beyond the scheduled dosing time (i.e., the time is past 14:00), the subject would resume dosing with the evening dose at approximately 20:00.

10.6 Discontinuation of Study Participation (Treatment Cohort)

If after review of a marketing application, local health authorities decline to approve, or if clinical benefit is not demonstrated for the use of VX-661 in combination with ivacaftor for the treatment of CF in populations enrolled in Study VX14-661-110, subjects with the relevant *CFTR* genotypes may be discontinued after communication to investigators and IRBs/IECs of the risks/benefits related to the safety and efficacy observed for the subset of subjects. In addition, if evaluation of efficacy data from the Phase 3 studies suggests that the VX-661/ivacaftor treatment does not provide clinically meaningful benefit for a population enrolled in Study VX14-661-110, Vertex may recommend that subjects with relevant *CFTR* genotypes discontinue from the Treatment Cohort of the study.

Subjects who become eligible to receive commercially-available VX-661/ivacaftor by prescription of a physician may be discontinued from this rollover study at the discretion of the sponsor. If a subject is continuing onto commercially available VX-661/ivacaftor, the Early Treatment Termination Visit ([Section 8.1.1.3](#)) will be completed before dosing with commercial drug begins, and the Safety Follow-up Visit ([Section 8.1.1.2](#)) will not be required.

Subjects may be discontinued from the Treatment Cohort at any time due to safety reasons. If a cataract or lens opacity is identified and determined to be clinically significant by the ophthalmologist after dosing, the subject will be notified. After discussion with the site principal investigator and in collaboration with the Vertex medical monitor, the subject may elect to continue or discontinue the study. If the subject discontinues study drug, they should complete the Early Treatment Termination Visit and Safety Follow-up Visit (see [Section 8.1.1.3](#) for Early Treatment Termination). If the subject continues, more frequent ophthalmologic monitoring should be considered.

10.7 Packaging and Labeling

Study drug tablets will be supplied in blister cards by Vertex. Study drug labeling will be in compliance with applicable local and national regulations. Additional details regarding packaging, labeling, and dispensing for VX-661 and ivacaftor will be included in the Pharmacy Manual.

10.8 Study Drug Supply, Storage, and Handling

Blister cards must be stored at room temperature according to [Table 10-3](#) and to the instructions provided in the Pharmacy Manual. While at the clinical site, the investigator, or an authorized

designee (e.g., a licensed pharmacist), will ensure that all investigational product is stored in a secured area, under recommended storage conditions, and in accordance with applicable regulatory requirements. To ensure adequate records, all study drugs will be accounted for in [Section 10.9](#).

Instructions regarding the storage and handling of study drug after dispensation to subjects will be provided to sites in the Pharmacy Manual.

Table 10-3 Identity of Study Drugs, Dosage, and Storage

Drug Name	Strength/Formulation/Route	Dosage	Storage Condition
VX-661/ivacaftor fixed-dose tablet	100-mg/150-mg tablet; oral	100 mg/ 150 mg, morning dose	≤25°C (77°F) with excursions to 30°C (86°F)
Ivacaftor	150-mg tablet, oral	150 mg, evening dose	≤25°C (77°F) with excursions to 30°C (86°F)

10.9 Drug Accountability (Treatment Cohort)

The pharmacist or designated study site staff will maintain information regarding the dates and amounts of (1) study drug received, (2) study drug dispensed to the subjects, and (3) study drug returned by the subjects. Subjects will be instructed to return all used and unused materials associated with the study drug to the site. These materials will be retained at the site according to instructions provided by Vertex or its designee until inventoried by the study monitor. The study monitor will review study drug records and inventory throughout the study.

10.10 Disposal, Return, or Retention of Unused Drug (Treatment Cohort)

The study site staff or pharmacy personnel will retain all materials returned by the subjects until the study monitor has performed drug accountability. The site monitor will instruct the site when it is appropriate to return or destroy study drug. If the site monitor authorizes destruction at the study site, the investigator, or designee, must ensure that the materials are destroyed in compliance with applicable environmental regulations, institutional policy, and any special instructions provided by Vertex. Destruction will be adequately documented.

10.11 Compliance (Treatment Cohort)

To ensure treatment compliance, the investigator or designee will supervise all study drug dosing that occurs at the site. At each visit, site personnel will review that the subject is compliant with study drug dosing and remind the subject of study drug dosing requirements. Compliance will also be assessed by ongoing study drug count.

If a subject demonstrates continued noncompliance of study drug dosing despite educational efforts, the investigator should contact the medical monitor to discuss discontinuation of the subject from the study.

10.12 Blinding and Unblinding

This will be an open-label study. However, subjects should not be informed of their study-related spirometry results during the study regardless if the subject has prematurely discontinued treatment.

[figure not shown]
11 ASSESSMENTS

11.1 Timing of Assessments

The timing of assessments is shown in [Table 3-1](#) (Treatment Cohort) and [Table 3-2](#) (Observational Cohort).

If study drug is not administered on the day of the visit (i.e., study drug interruption), assessments will still be collected unless otherwise noted.

The CFQ-R questionnaire must be completed before any other assessment at the clinic visits. For the remaining assessments, the following assessments must be performed in the following order when more than 1 assessment is required at a particular time point.

- 
2. standard 12-lead ECG recording
 3. vital signs and pulse oximetry (interchangeable order is acceptable)
 4. spirometry
 5. safety laboratory assessments and PK sampling (i.e., blood draws)

All other assessments may be completed in any order as shown in [Table 3-1](#) and [Table 3-2](#).

11.2 Informed Consent/Assent

Each subject of age of consent (per local requirements) must sign and date a study-specific ICF before any study-specific procedures can be performed **and before the subject receives the first dose of study drug**. Subjects not of age of consent must assent, if applicable per local requirements, to participate in the study, and the subject's parent or legal guardian must sign and date a study-specific ICF **before any study-specific procedures can be performed, and before the subject receives the first dose of the study drug**. The consent/assent forms will comply with all applicable regulations governing the protection of human subjects. An ICF and Assent Form, approved by Vertex and the site's institutional review board (IRB) or independent ethics committee (IEC), must be used.

Subjects who re-enroll in the Treatment Cohort must re-consent/assent ([Table 3-1](#)) **before any study-specific procedures can be performed and before the subject receives the first dose of the study drug**.

11.3 Assigning Subject Number

All subjects will retain their subject number from the parent study.

11.4 Subject and Disease Characteristics

Subject and disease characteristics include the following: demographics, medical history, height, and weight. Select demographic and baseline characteristic data and medical history will be derived from the parent study.

Age, sex, race, and ethnicity will be derived from the parent study because these data are required for the normalization of spirometry values using either the Wang or Hankinson methods ([Section 11.7.1](#)).

11.5 Pharmacokinetics (Treatment Cohort Only)

11.5.1 Blood Sampling

Blood samples will be collected as shown in [Table 3-1](#) for the determination of the plasma concentrations of VX-661, M1-661, ivacaftor, and M1-ivacaftor. Blood samples must be collected within 60 minutes before dosing.

Samples from the PK sampling will be kept frozen by Vertex or its designee until all analyses have been completed and then disposed of according to Vertex or designee standard operating procedures.

For each visit with a PK blood draw, a record of study drug administration will be collected as described in [Section 10.2](#). The collection date and time that each PK blood sample is drawn will also be recorded.

[figure not shown]
Details on sample collection, processing, and shipping will be provided in a separate protocol-specific Laboratory Manual.

11.5.2 Processing and Handling of Pharmacokinetic Samples

Detailed procedures for the collection of blood samples and further procedures for processing and handling of samples for PK analysis will be provided in the Laboratory Manual. The shipment address and assay laboratory contact information will be provided to the investigational site before initiation of the study.

11.5.3 Bioanalysis

Samples will be analyzed using a validated analytical method in compliance with Vertex or designee standard operating procedures. A description of the assay and validation data will be provided in separate reports.

11.7 Efficacy

11.7.1 Spirometry (Treatment Cohort)

Spirometry will be performed according to the American Thoracic Society Guidelines³², according to the additional guidelines that follow.

Pre-bronchodilator spirometry is defined as spirometry testing performed for subjects who have

- withheld their short-acting bronchodilators (e.g., albuterol) or anticholinergic (e.g., ipratropium bromide [Atrovent[®]]) for more than 4 hours before the spirometry assessment;
- withheld their long-acting bronchodilator (e.g., salmeterol) for more than 12 hours before the spirometry assessment; and
- withheld their once-daily, long-acting bronchodilator (e.g., tiotropium bromide [Spiriva[®]]) for more than 24 hours before the spirometry assessment.

All spirometry assessments should be performed "pre-bronchodilator." During the Treatment Period, spirometry assessments must be performed before dosing. In the event that a subject forgets to withhold bronchodilator(s), spirometry should be performed according to the following:

- If a subject's Day 1 spirometry is pre-bronchodilator, but, on a subsequent visit, the subject forgets to withhold bronchodilator use, a post-bronchodilator spirometry assessment will be obtained for that visit only, and the visit will not be rescheduled.
- If, on Day 1, the subject forgets to withhold his/her dose of bronchodilator, spirometry should be performed post-bronchodilator, and all subsequent spirometric measurements should be performed post-bronchodilator.
- Each spirometry assessment will be recorded in the source documents as pre- or post-bronchodilator.

All sites will be provided with spirometers to be used for all study assessments. Spirometry data will be transmitted to a centralized spirometry service for quality review.

The parameters listed below will be normalized using the standards of Wang et al.³³ (for female subjects aged 12 to 15 years [inclusive] and male subjects aged 12 to 17 years [inclusive]) or Hankinson et al.³⁴ (for female subjects aged 16 years and older and male subjects aged 18 years and older).

- FEV₁ (L)
- Forced vital capacity (FVC) (L)
- FEV₁/FVC (ratio)
- Forced expiratory flow (FEF_{25%-75%}) (L/s)

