^f **Initial enrollment:** The Day 1 Visit of Study VX14-661-110 will be on the **same day** as the last scheduled visit of the parent study for subjects at Study VX14-661-110 sites that have been activated by the time the subject has completed the last scheduled visit in the parent study. Subjects at these active sites will NOT have to repeat any Study VX14-661-110 Day 1 assessments that were specified to be performed at the last scheduled visit in the parent study. Subjects who were enrolled but had Day 1 study drug administration procedures ([Section 10.2](#)) delayed will have to repeat the safety ([Section 11.8](#)) and spirometry ([Section 11.7.1](#)) assessments that were specified to be performed at the Day 1 Visit before receiving their first dose of study drug. However, the Day 1 Visit of Study VX14-661-110 **will NOT coincide** with the last scheduled visit of the parent study for subjects at Study VX14-661-110 sites that have NOT been activated by the time the subject has completed the last scheduled visit in the parent study. Subjects at these nonactive sites will have to repeat any Study VX14-661-110 Day 1 assessments that were specified to be performed at the last scheduled visit in the parent study.

^g **Re-enrollment:** Subjects who re-enroll in the Treatment Cohort will complete the Returning Visit and will resume treatment with VX-661/ivacaftor at the next study day after their previous treatment discontinuation from Study VX14-661-110. If the timepoint coincides with a scheduled Study VX14-661-110 visit (± 5 days), only the Returning Visit assessments will be completed. Subjects who were re-enrolled but had their Returning Visit study drug administration procedures ([Section 10.2](#)) delayed will have to repeat the safety ([Section 11.8](#)) and spirometry ([Section 11.7.1](#)) assessments that were specified to be performed at the Returning Visit before receiving their first dose of study drug.

Table 3-1 Study VX14-661-110: Treatment Cohort

Event/Assessment ^a	Day -28 to Day -1	Treatment Period ^b						ETT Visit/ Departing Visit (Within 7 Days of Last Dose of Study Drug) ^{b,c,d,e}	Safety Follow-up Visit 28 (± 7) Days After Last Dose ^{c,d,e}
		Day 1 ^f / Returning Visit ^{b,g}	Day 15 (± 3 days)	Weeks 8, 16, 24, 36 (± 5 days)	Week 48 (± 5 days)	Weeks 60, 72, 84 (± 5 days)	Week 96 (± 5 days)		
Informed consent/assent	X ^h	X ^h							
Inclusion and exclusion criteria review		X							
CFQ-R ⁱ		X	X	X	X	X	X	X	X

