8.1.1 Treatment Cohort (Eligible Subjects 12 Years of Age and Older)

8.1.1.1 Treatment Period

After obtaining informed consent and assent (where applicable), and eligibility has been confirmed, subjects will receive VX-661 100 mg/ivacaftor 150-mg FDC tablet qd in the morning and ivacaftor 150-mg tablet qd in the evening. Study drug will be administered for approximately 96 weeks.

Initial Enrollment

Timing of Treatment Cohort Day 1 Visit in Study VX14-661-110 Active Sites

The Day 1 Visit of Study VX14-661-110 will be on the **same day** as the last scheduled visit of the parent study for subjects at Study VX14-661-110 sites that have been activated by the time the last scheduled visit of the parent study has been completed. Subjects at these active sites MAY have to repeat any Day 1 assessments of Study VX14-661-110 that were specified to be performed at the last scheduled study visit of the parent study. Assessments for the Treatment Cohort are listed in [Table 3-1](#).

Subjects who were enrolled but had Day 1 study drug administration procedures ([Section 10.2](#)) delayed will have to repeat the safety ([Section 11.8](#)) and spirometry ([Section 11.7.1](#)) assessments that were specified to be performed at the Day 1 Visit before receiving their first dose of study drug.

Timing of Day 1 Visit in Study VX14-661-110 Nonactive Sites

The Day 1 Visit of Study VX14-661-110 **will NOT coincide** with the last scheduled visit of the parent study for subjects at Study VX14-661-110 sites that have NOT been activated by the time the last scheduled visit of the parent study has been completed. Subjects at these nonactive sites will have to repeat any Study VX14-661-110 Day 1 assessments that were specified to be performed at the last scheduled visit of the parent study. Assessments for the Treatment Cohort are listed in [Table 3-1](#).

Re-enrollment

Subjects who re-enroll in the Treatment Cohort will complete the Returning Visit and resume treatment with VX-661/ivacaftor at the next study day after their previous treatment discontinuation from Study VX14-661-110. If the timepoint coincides with a scheduled Study VX14-661-110 visit (± 5 days), only the Returning Visit assessments will be completed. Assessments for the Treatment Cohort are listed in [Table 3-1](#).

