12.3 Statistical Analysis

12.3.1 General Considerations

Continuous variables will be summarized using the following descriptive summary statistics: the number of subjects (n), mean, SD, median, minimum value (min), and maximum value (max).

Categorical variables will be summarized using counts and percentages.

Baseline value, unless otherwise specified, for efficacy and safety analyses, will be defined as the most recent non-missing measurement (scheduled or unscheduled) collected before the first dose of VX-661/ivacaftor or ivacaftor alone (in the parent study or Study VX14-661-110, but

after the washout period, if applicable). For subjects who received VX-661 and ivacaftor combination therapy in the parent study, the baseline will be the same as the baseline in the parent study. For subjects who received placebo or ivacaftor in the parent study and transitioned to VX-661/ivacaftor in Study VX14-661-110, the baseline will be the baseline in Study VX14-661-110. For subjects from Study VX14-661-108, the parent study baseline will be the baseline for Treatment Period 2 in Study VX14-661-108. For subjects from Study VX13-661-103, the parent study baseline will be the baseline in the Open-label Phase of Study VX13-661-103 for subjects who participated in the Open-label Phase or the baseline in Study VX14-661-110 for subjects who did not participate in the Open-label Phase of Study VX13-661-103.

Change (absolute change) from baseline will be calculated as postbaseline value - baseline value.

Relative change from baseline will be calculated as (postbaseline value - baseline value)/baseline value.

Efficacy Analysis Period will include the time from the first dose of VX-661/ivacaftor or ivacaftor alone (in the parent study or Study VX14-661-110, but after the washout period, if applicable) to the last scheduled efficacy visit in Part of Study VX14-661-110. For subjects who participate in another qualified Vertex study before completing Study VX14-661-110 assessments and re-enroll in Study VX14-661-110, the Efficacy Analysis Period will exclude the time between the last dose before the discontinuation from Study VX14-661-110 and the first dose after re-enrollment in Study VX14-661-110.

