12.3.2 Overview of Analysis Strategies

- Study VX14-661-110 data will not be analyzed in isolation as patients received different durations of treatment in the parent studies. Study VX14-661-110 data will be integrated with the parent study data for each subject from the first active dose of VX-661/ivacaftor or ivacaftor alone (after the washout period, if applicable).
- The analysis baseline will be the last non-missing measurement prior to the first active dose of VX-661/ivacaftor or ivacaftor alone [in the parent study (after the washout period, if

applicable) or Study VX14-661-110]. All post-baseline measurements will be mapped to the uniform analysis visit windows based on the study days counted from the first active dose of VX-661/ivacaftor or ivacaftor alone (after the washout period in the parent study, if applicable) to make the results more comparable and interpretable.

- For subjects in Study VX14-661-110, the safety analyses will be performed on all of the subjects pooled together. The efficacy analysis will be performed on each CFTR mutation group separately (*F508del/F508del*, *F508del/Residual Function*, and *F508del/Gating*).

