- Derivations of measurements at scheduled visits per specified visit windowing rules;
- Derivations of baseline/last on-treatment measurements;
- Derivations of the maximum/minimum on-treatment values and maximum/minimum changes from baseline values for safety analyses;
- Data listings where appropriate.

Treatment-emergent (TE) Period will include the time from the first active dose of VX-661/ivacaftor or ivacaftor alone (in the parent study or Study VX14-661-110, but after the washout period, if applicable) to the Safety Follow-up Visit in Part A or 28 days after the last dose of the study drug for subjects who do not have a Safety Follow-up Visit or who have their Safety Follow-up Visit more than 35 days after the last dose in Part A of Study VX14-661-110. For subjects who participate in another qualified Vertex study before completing Part A of Study VX14-661-110 (96 weeks) and re-enroll in Study VX14-661-110, the TE Period will exclude the time spent in the other study.

110 Treatment-Emergent (TE) Period is defined as the time from 1st dose of study drug in Part A to SFU in Part A or 28 days after the last dose of the study drug for subjects who do not have a SFU Visit or who have their SFU Visit more than 35 days after the last dose in Part A. For subjects who participate in another qualified Vertex study before completing Part A (96 weeks) and re-enroll in Study 110, the TE Period will exclude the time spent in the other study. The **efficacy analysis baseline** is defined as the most recent non-missing measurement (scheduled or unscheduled) collected prior to the first dose of study drug in the parent studies for all subjects, except for subjects randomized to the placebo arm in Study 106.

The efficacy analysis baseline for subjects randomized to the Study 106 placebo arm is defined as the most recent non-missing measurement (scheduled or unscheduled) collected prior to the first dose of study drug in Study 110.

The **safety analysis baseline**, unless otherwise specified, is defined as the last non-missing assessment prior to the first dose of active treatment (TEZ/IVA or IVA) from the parent study (after the wash-out period, where applicable) or Study 110, whichever is earlier.

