9.6.2 Analysis of Efficacy Endpoints

Most continuous endpoints during 110 Efficacy Analysis Period will be analyzed for subjects in 106/110 ES and 108/110 ES using a mixed-effects model for repeated measures (MMRM) with similar specification as in the parent study SAP/CSR, if applicable. However, these MMRM analysis will be restricted to the last visit at which the total number of subjects is approximately 70% of subjects from the respective parent study.

These continuous endpoints during 110 Efficacy Analysis Period will also be descriptively summarized for subjects in FAS who roll over from Study 103 and 111, where the patients carry *F/F* mutation.

No hypothesis testing will be done for between-group comparisons.

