9.6.2.1 Absolute Change in Percent Predicted FEV₁ from Baseline

9.6.2.1.1 Subjects in 106/110 ES

The MMRM for 106/110 ES during 110 Efficacy Analysis Period will have the absolute change in ppFEV₁ from baseline (including all measurements up to Week 96 [inclusive], both on-treatment measurements and measurements after treatment discontinuation) as the dependent variable and the following fixed effects: treatment (PBO-TEZ/IVA, TEZ/IVA), visit, and treatment-by-visit interaction, sex and age group at screening (<18, ≥18 years old), parent study baseline ppFEV₁, and parent study baseline ppFEV₁-by-visit interaction.

The repeated-measures analysis will be based on the restricted maximum likelihood (REML) method assuming an unstructured (UN) covariance structure to model the within-subject errors. The denominator degrees of freedom will be based on the method proposed by Kenward-Roger. If the model fails to converge due to the UN covariance assumption, a compound symmetry (CS) covariance structure will be used to model the within-subject errors. In the MMRM approach, assuming that the data are missing at random, no imputation of missing data will be performed.

The number of subjects, least-squares (LS) means at scheduled visits within each treatment group along with the corresponding standard error (SE) and 95% confidence interval (CI) will be presented.

The LS means (±95% CI) for absolute change from baseline at each visit will also be plotted by treatment group.

In addition, the descriptive statistics for observed values and absolute changes from baseline in ppFEV₁ by treatment group will be presented at scheduled visits during 110 Efficacy Analysis Period.

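### Does tying later spirometry to the bronchodilator status of Study 110 Day 1, while measuring ppFEV1 change from the parent-study baseline, require a change to the analysis?

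*Protocol*

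**What the plan says.** Protocol 11.7.1 makes pre-bronchodilator testing the default and allows for two lapses. If Day 1 was pre-bronchodilator and the subject later forgets to withhold, a post-bronchodilator test is accepted for that visit only. If the lapse is on Day 1 itself, "spirometry should be performed post-bronchodilator, and all subsequent spirometric measurements should be performed post-bronchodilator". Both rules take Study 110 Day 1 as their reference.

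The analysis uses a different reference. SAP 9.1 takes the efficacy baseline "prior to the first dose of study drug in the parent studies for all subjects, except for subjects randomized to the placebo arm" of Study 106; only that arm uses the last value before the first Study 110 dose. The ppFEV1 model for the Study 106 rollovers takes all records, "including all measurements up to Week 96 [inclusive], both on-treatment measurements and measurements after treatment discontinuation", and the Study 108 model is similar. SAP 9.6.2 cuts the MMRM off early, so that it is "restricted to the last visit at which the total number of subjects is approximately 70% of subjects from the respective parent study", but this does not limit the descriptive tables. The SAP does not mention bronchodilators.

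The protocol's own baseline text is mixed. Section 12.3.1 states: "For subjects who received placebo or ivacaftor in the parent study and transitioned to VX-661/ivacaftor in Study VX14-661-110, the baseline will be the baseline", meaning that of Study 110. Section 12.3.2 counts from the first dose of either active regimen: "The analysis baseline will be the last non-missing measurement prior to the first active dose of VX-661/ivacaftor or ivacaftor alone".

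The timing of Day 1 also matters. Where the site is already active, Day 1 is the last parent-study visit, and Table 3-1 footnote f says "Subjects at these active sites will NOT have to repeat any Study VX14-661-110 Day 1 assessments" (section 8.1.1.1 says they may have to). If dosing is delayed, section 8.1.1.1 requires repeating the safety and spirometry "assessments that were specified to be performed at the Day 1 Visit before receiving their first dose of study drug".

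**The concern.** The protocol treats bronchodilator status as something to hold constant within a subject, but holds it constant against a visit that is the analysis baseline for only one group. Suppose a subject was tested pre-bronchodilator at the parent baseline and post-bronchodilator on Study 110 Day 1. Under the rule, every later change from baseline then includes the bronchodilator response: Day 15 and Weeks 8, 16, 24, 36, 48, 60, 72, 84 and 96, which is 10 visits. The opposite mismatch lowers the change in the same way. Such an offset persists from visit to visit and does not average out within the subject.

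The groups that could be affected are the Study 106 TEZ/IVA group, the three Study 108 groups, and the descriptive summaries for Studies 103 and 111. Their within-group means are the long-term efficacy result, and there is no concurrent control in which an offset would show. No table, model term or sensitivity analysis uses the status.

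**Working it through.** **Plan's own figure.** SAP 6.2 gives enrolment by parent study: 23 + 464 + 159 + 227 + 138 + 33 = 1,044, which matches the stated total. No SD, effect size or power is given for ppFEV1, so there is nothing further to reproduce.

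**Who is exposed.** ppFEV1 change is planned for rollovers from Studies 106, 108, 103 and 111: 464 + 227 + 23 + 33 = 747. The Study 106 placebo share is not given. Taking one third to one half (assumed) gives 155 to 232 subjects, which leaves 592 to 515 of 747 (79% to 69%) with a parent-study baseline. This is how many the Day 1 rule does not protect, not how many are mismatched.

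**When an offset arises.** Set status at the parent baseline against status on Study 110 Day 1:

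- pre, then pre: matched; a later lapse affects one visit.
- post, then post: matched, and the Day 1 rule preserves the match.
- pre, then post: positive offset at all later visits.
- post, then pre: negative offset at later visits, apart from any lapse.

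Only the last two matter, and they act in opposite directions. With pre-bronchodilator testing as the default, the third needs a lapse on one particular day. The documents do not give the parent-study rules. If those studies carried the same rule (assumed), a post-bronchodilator parent baseline at an active site would lead to a post-bronchodilator Day 1, which is the second, matched case.

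**Size.** Shift in a group mean = p × δ, where p is the share mismatched in one direction and δ the bronchodilator response in ppFEV1 points. Neither is in the documents; both are assumed.

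- 2% × 3 = 0.06
- 5% × 5 = 0.25
- 10% × 8 = 0.80
- Opposite mismatches: (5% − 2%) × 5 = 0.15

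As a round reference, a one-point shift needs p = 1/δ: 20% of the group mismatched in one direction at 5 points, or 12.5% at 8 points.

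**Numbers of subjects at 2% and 10%.**

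- Study 108: 227 × 0.02 = 4.5; 227 × 0.10 = 22.7
- Studies 103 and 111 together: 56 × 0.02 = 1.1; 56 × 0.10 = 5.6
- Study 106 TEZ/IVA, taking 40 to 60% of 464 (assumed): 464 × 0.4 × 0.02 = 3.7; 464 × 0.6 × 0.10 = 27.8

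**Single-visit lapses.** At 2% × 3 to 5% × 8 they add 0.06 to 0.40 points at the visit concerned. They would occur under any choice of baseline, and 11.7.1 knowingly accepts them rather than rescheduling.

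**What a matched-records analysis would do.** A pre-then-post subject whose tests follow the rule has no matching record. A post-then-pre subject has one only at a visit with a lapse. Both kinds of subject largely leave the analysis. For a simple mean, the standard error grows by 1/√(1 − p): 1.010 at 2% and 1.054 at 10%. The MMRM would lose less from excluding single visits, because it borrows from a subject's other visits. Repeating absolute and relative change in both efficacy sets would be four more MMRMs.

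**The case for a change.** The strongest case for acting is that the offset is systematic, that no control arm would reveal it, and that showing it to be small is the sponsor's task. Protocol 12.3.3 promises listings of all subject data, but that sentence sits under background characteristics, and a listing does not compare a record's status with its baseline. Section 11.7.1 places the status in source documents, and nothing says that it reaches the analysis data. At sites not yet active, Day 1 is a fresh test. With delayed dosing, 11.7.1 does not say which test sets the status.

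Much of this stands. No planned output identifies or summarises mismatched records, and the documents do not show that the effect is small. What does not follow is a different result. The all-records MMRM would remain the main analysis in any case. The matched-records analysis cannot isolate the offset: it removes bronchodilator users, who may respond differently, so a changed estimate would mix offset with selection, and an unchanged one could hide cancellation. Obtaining the status may also mean going back to source documents, including those of the parent studies.

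It might also be said that the SAP widens the gap beyond the protocol. For the Study 108 placebo group this is not clear. SAP 7.2 shows that the group includes the TEZ/IVA-then-placebo sequence, and under Protocol 12.3.1 those subjects fit both the sentence for combination therapy and the one for placebo. For ivacaftor subjects the protocol disagrees with itself. The choice of baseline is a separate question from bronchodilator status.

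**Conclusion.** No change to the plan follows. The two documents do use different reference points, and a subject whose status differs between them could carry an offset through follow-up. On assumed inputs, that moves a group mean by 0.06 to 0.80 ppFEV1 points, with 0.25 at 5% mismatched and a 5-point response, and less if mismatches run both ways. The upper end needs one subject in ten mismatched in the same direction with an 8-point response. Efficacy is a secondary objective, and SAP 9.6.2 plans no between-group test.

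The Day 1 rule is a fair trade-off: it keeps each subject's Study 110 series on one footing and avoids losing visits. Which test counts as Day 1 after delayed dosing is a gap that analysts can fill sensibly. The natural reading is the last test before the first Study 110 dose, which SAP 9.1 already takes as baseline for the Study 106 placebo arm. If the status is in the database, mismatched records can be counted at any time without touching a prespecified test. That is an optional check, and nothing in the documents shows that it would alter a reported conclusion.

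This rests on unknowns that the documents cannot settle: the frequency and direction of mismatches, the size of the response, and the parent-study rules. A mismatch far more common than the assumed range would be a reason to look again.
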